4.1 Inclusion criteria

Only those who meet all the conditions listed in this column can be considered for inclusion in this research:

- (1) Steroid-sensitive nephrotic syndrome with frequent relapse (FRNS) or steroid dependence (SDNS);
- (2) Age: 2-18 years old;
- (3) Normal renal function: $eGFR \geq 90 \text{ mL/min/1.73m}^2$;
- (4) At the time of enrollment, urinary protein $< 1+$ or urinary protein/creatinine $< 0.2 \text{ g/g}$ ($< 20 \text{ mg/mmol}$) in the morning for 3 consecutive days or more;
- (5) No use of tacrolimus, mycophenolate mofetil, cyclosporine A, rituximab or cyclophosphamide within 2 years before enrollment;

4.2 Exclusion criteria

Anyone with one of the following conditions cannot be included in this research:

- (1) Steroid-resistant nephrotic syndrome (SRNS);
- (2) Family history of nephrotic syndrome, chronic glomerulonephritis or uremia;
- (3) Leukopenia (leukocyte $\leq 3.0 \times 10^9/\text{L}$);
- (4) Moderate and severe anemia (hemoglobin $< 9.0 \text{ g/dL}$);
- (5) Thrombocytopenia (platelet count $< 100 \times 10^{12}/\text{L}$);

- (6) Those with positive HBV serological indexes (HBsAg or/and HBeAg or/and HBcAb), positive HCV or abnormal liver function (ALT or total bilirubin exceeding 2 times or more of the upper limit, with a continuous increase for 2 weeks);
- (7) There are chronic active infections such as Epstein-Barrvirus, cytomegalovirus or Mycobacterium tuberculosis, and the usage of steroids and immunosuppressive agents may aggravate the state of an illness;
- (8) Secondary nephrotic syndrome (such as purpura nephritis ,lupus nephritis,etc);
- (9) Those who with hematological or endocrine system diseases as well as serious organs illness such as heart, liver or kidney;
- (10) Other autoimmune diseases or primary immunodeficiency or tumors;
- (11) Those who was known be sensitized to tacrolimus, mycophenolate mofetil, glucocorticoids or any ingredient of the above drugs;
- (12) Those who have participated in other clinical trials within three months before enrollment;
- (13) Those who was not suitable for participating this study judged by investigator;

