4.4 Withdrawal criteria

Patients are free to withdraw from the trial at any time without any reason.

Patients must withdraw from this research in the following conditions:

- Withdrawal of the Informed Consent Form;
- Violation of the inclusion criteria or compliance with the exclusion criteria;
- No administration of the test drug according to the Protocol for 14 consecutive days due to various reasons;
- For two consecutive times, the measured value of SCr with an interval of at least 4 weeks has increased more than twice the baseline, and eGFR < 60mL/min.1.73m²;
- The target concentration of tacrolimus or mycophenolate mofetil can not be reached after dose adjustment for one month;
- ALT or total bilirubin levels reach more than 2 times of the upper limit after medication, with a continuous increase for 2 weeks; if ALT or total bilirubin levels still rise to more than 2 times of the upper limit after 2 weeks of liver protection drug treatment, stop the test drug. In case of no recovery after 2 weeks of drug withdrawal, the patient shall withdraw from the test;

- Occurrence of unknown adverse events of unacceptable nature, severity and/or duration, or occurrence of known unacceptable adverse events or the occurrence frequency exceeding expectations;
- The clinical events or safety-affecting events result in withdrawal from the clinical trial, and the investigators believe that such subjects shall withdraw from the trial;
- If pregnancy occurs during treatment, withdraw from the trial;
- Unauthorized use of drugs prohibited by this research (see "5.3 Concomitant medication");

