4.6 Relevant definitions in inclusion and exclusion criteria

4.6.1 Steroid-sensitive nephrotic syndrome (SSNS): Complete remission after 4 weeks of prednisone or prednisolone at standard dose [2mg/kg.d or 60mg/m². d].

- 4.6.2 Steroid-resistant nephrotic syndrome (SRNS):** Lack of complete remission at 4 weeks of therapy with daily prednisone or prednisolone at standard dose [2mg/kg.d or 60mg/m².d].
- 4.6.3 Steroid-dependent nephrotic syndrome (SDNS):** Two consecutive relapses during therapy with prednisone or prednisolone (either at full dose or during tapering) or within 15 days of prednisone or prednisolone discontinuation.
- 4.6.4 Frequently relapsing nephrotic syndrome (FRNS):** ≥ 2 relapses per 6 months within 6 months of disease onset or 24 relapses per 12 months in any subsequent 12-month period.
- 4.6.5 Secondary nephrotic syndrome:** It refers to the nephrotic syndrome with clear causes. Secondary nephrotic syndrome can be caused by autoimmune diseases (such as systemic lupus erythematosus), diabetes, infections (such as bacteria and hepatitis B virus), circulatory system diseases, drug poisoning, etc.

5. Test drugs and their allocation

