4.5.2. Exclusion criteria

Anyone with one of the following conditions cannot be included in this research:

- (1) Steroid-resistant nephrotic syndrome (SRNS).
- (2) Family history of nephrotic syndrome, chronic glomerulonephritis or uremia.
- (3) Leukopenia (leukocyte $\leq 3.0 \times 10^9/L$).
- (4) Moderate and severe anemia (hemoglobin < 9.0 g/dL).
- (5) Thrombocytopenia (platelet count $< 100 \times 10^{12}/L$).
- (6) Those with positive HBV serological indexes (HBsAg or/and HBeAg or/and HBcAb), positive HCV or abnormal liver function (ALT or total bilirubin exceeding 2 times or more of the upper limit, with a continuous increase for 2 weeks).
- (7) There are chronic active infections such as Epstein-Barrvirus, cytomegalovirus or Mycobacterium tuberculosis, and the usage of steroids and immunosuppressive agents may aggravate the state of an illness.

- (8) Secondary nephrotic syndrome (such as purpura nephritis, lupus nephritis, etc).
- (9) Those who with hematological or endocrine system diseases as well as serious organs illness such as heart, liver or kidney.
- (10) Other autoimmune diseases or primary immunodeficiency or tumors.
- (11) Those who was known be sensitized to tacrolimus, mycophenolate mofetil, glucocorticoids or any ingredient of the above drugs.
- (12) Those who have participated in other clinical trials within three months before enrollment.
- (13) Those who was not suitable for participating this study judged by investigator.

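### The platelet exclusion is printed in 10^12/L, 1,000 times the scale of the neighbouring leukocyte limit, so read literally it excludes every child and empties the per-protocol set

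*Protocol*

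**What the plan says.** Protocol 4.2 opens with a strict rule: "Anyone with one of the following conditions cannot be included in this research". Item (5), "Thrombocytopenia (platelet count", is set at less than 100 x 10^12/L. Item (3), "Leukopenia (leukocyte", is set at 3.0 x 10^9/L or less. SAP 4.5.2 repeats both items with the same exponents.

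The exclusion list also has consequences after entry. Protocol 4.4 and SAP 4.5.4 make withdrawal mandatory for "Violation of the inclusion criteria or compliance with the exclusion criteria". Protocol 11.1 and SAP 7.1 admit to the PPS only cases that meet none of the exclusion criteria.

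On the secondary matter, Protocol 4.6.4 and SAP 4.5.6 define frequently relapsing nephrotic syndrome (FRNS) by two alternatives. One is at least 2 relapses per 6 months within 6 months of onset. The other reads "24 relapses per 12 months in any subsequent 12-month period". Under Protocol 4.1(1) and SAP 4.5.1(1), steroid dependence (SDNS) is a separate route into the trial.

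**The concern.** Two blood-count limits in one list use scales that differ by a factor of 1,000, and the heading of the platelet item shows that it was meant to pick out children with low counts. With the printed exponent it picks out everyone.

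This is an operative threshold. It decides entry, it can force withdrawal, and it decides PPS membership, while SAP Table 19 reports the primary endpoint for the PPS beside the full analysis set (FAS). Anyone who later checks eligibility against the text, whether an auditor, a programmer or a second statistician, cannot reproduce the PPS. If sites used a sensible limit, neither document says what it was or whether it was the same at every site.

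**Working it through.** **Inputs**
- Platelet limit: below 100 x 10^12/L (Protocol 4.2(5), SAP 4.5.2(5)).
- Leukocyte limit: 3.0 x 10^9/L or less (Protocol 4.2(3), SAP 4.5.2(3)).
- Leukocyte limit in the mycophenolate dose-adjustment rule: 3000 per μL (Protocol 5.2.4.1, SAP 5.2.4.1).
- Platelet range: not given in either document. I assume 10 to 2,000 x 10^9/L, chosen to be wide.

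**Step 1: confirm the leukocyte scale.** 3.0 x 10^9/L ÷ 10^6 μL/L = 3,000 per μL. This agrees with the figure in the dose-adjustment rule, so the 10^9/L scale is supported within the documents.

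**Step 2: put the platelet limit on that scale.** 100 x 10^12/L ÷ 10^9 = 100,000, that is, 100,000 x 10^9/L. Per μL it is 100 x 10^12 ÷ 10^6 = 100,000,000. The ratio of the two scales is 10^12 ÷ 10^9 = 1,000.

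**Step 3: apply the printed limit.** Values of 10, 50, 100, 150, 300, 450, 1,000 and 2,000 x 10^9/L are all below 100,000 x 10^9/L, so all meet the exclusion. The printed limit is 100,000 ÷ 2,000 = 50 times the top of the assumed range. The result therefore does not depend on where in that range the children lie.

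**Step 4: follow it through the analysis sets.** Every child meets an exclusion criterion, and the PPS requires that none is met, so the literal PPS has no members. The FAS definition does not state that condition, and the safety set expressly keeps some children who breach eligibility.

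**Step 5: the FRNS count, if 24 is what is printed.** 365.25 ÷ 24 = 15.2 days per relapse. The first branch, 2 in 6 months, is 4 a year, and 24 ÷ 4 = 6 times that rate. As a rough yardstick from the trial's own text, take 3 days of proteinuria to define a relapse (Protocol 7.2.4), then 5 to 7 days after the urine clears and 4 weeks at the next steroid step (Protocol 5.2.2). That makes 36 to 38 days, or 365.25 ÷ 38 = 9.6 to 365.25 ÷ 36 = 10.1 cycles a year. This is not a hard ceiling, because a child can relapse during treatment, but it shows that 24 is implausible. It does not show that 24 is what the plan prints.

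**The case against.** The strongest reply is that this is a clerical slip which misled nobody. The word thrombocytopenia and the adjacent 10^9/L limit show the intention, and SAP 4.1 reports enrolment at 12 sites as finished, so the printed limit cannot have been applied. Neither document describes an automated check on numeric laboratory limits. SAP Tables 109 and 110 list a recorded reason for leaving the PPS, and Table 111 takes deviations from an external file. All of this stands, and it limits the harm to documentation and to deriving the PPS reproducibly. It does not supply the limit that was used.

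A reader might infer that all the analysis sets are emptied. The documents do not support that. Only the PPS expressly requires that no exclusion criterion is met. The FAS takes in drop-outs and removes eliminated cases, and the elimination criteria (Protocol 4.3, SAP 4.5.3) concern compliance, cooperation and completing follow-up. A note under SAP Table 1 uses elimination in another sense, for children who complete but are not in the PPS. The FAS definition does not refer to that note, so I rest nothing on it.

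A reader might also infer that the FRNS definition is equally broken. That is not established. In text read from a PDF, a greater-or-equal sign followed by 4 can be misread as 24, and the second branch carries no inequality sign of its own. Against a misreading, the same sign before the 2 earlier in that sentence was read correctly, and 24 recurs in both documents. The recurrence is weak evidence, because the SAP largely repeats the protocol. Even if 24 is printed, the first FRNS branch and the SDNS route still work, so only children whose frequent relapses arise later and who qualify by neither would be affected.

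**Conclusion.** The platelet limit is wrong as written in both documents, by a factor of 1,000 against the leukocyte scale. Read literally, it makes every child ineligible and leaves the PPS empty. The only assumption is the platelet range, and the conclusion holds with a 50-fold margin at its upper end. A misread exponent is unlikely, since the same two-digit exponent appears in both documents and the 9 in the neighbouring item was read correctly in each.

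The practical consequence is that eligibility and PPS membership cannot be reproduced from the text. Sample size, power and alpha do not depend on the platelet limit or the relapse count. The FRNS figure remains a point to verify.

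**What to change.** 1. Reconcile the platelet unit with the leukocyte unit in Protocol 4.2(5) and SAP 4.5.2(5), and state the limit actually applied at enrolment. That limit is for the sponsor to supply from trial records.
2. Use the stated limit for the PPS eligibility check, and say so in SAP 7.1.
3. Check the 12-month relapse count in the source PDFs of Protocol 4.6.4 and SAP 4.5.6. If 24 is printed, reconcile it with the first branch (at least 2 per 6 months) and with the count used at enrolment. If it is not, no change is needed.

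The cost is a minor protocol amendment, which under Protocol 12.1 needs Ethics Committee approval before implementation, and a matching SAP edit. No analysis method changes.

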4.3 Elimination criteria

- Those who fail to take the test drugs as required, with a compliance <80% or >120%;
- Those who cannot cooperate well or complete the follow-up as planned, and those who change the drug dose at will;

4.4 Withdrawal criteria

Patients are free to withdraw from the trial at any time without any reason.

Patients must withdraw from this research in the following conditions:

- Withdrawal of the Informed Consent Form;
- Violation of the inclusion criteria or compliance with the exclusion criteria;
- No administration of the test drug according to the Protocol for 14 consecutive days due to various reasons;
- For two consecutive times, the measured value of SCr with an interval of at least 4 weeks has increased more than twice the baseline, and eGFR < 60mL/min.1.73m²;
- The target concentration of tacrolimus or mycophenolate mofetil can not be reached after dose adjustment for one month;
- ALT or total bilirubin levels reach more than 2 times of the upper limit after medication, with a continuous increase for 2 weeks; if ALT or total bilirubin levels still rise to more than 2 times of the upper limit after 2 weeks of liver protection drug treatment, stop the test drug. In case of no recovery after 2 weeks of drug withdrawal, the patient shall withdraw from the test;

- Occurrence of unknown adverse events of unacceptable nature, severity and/or duration, or occurrence of known unacceptable adverse events or the occurrence frequency exceeding expectations;
- The clinical events or safety-affecting events result in withdrawal from the clinical trial, and the investigators believe that such subjects shall withdraw from the trial;
- If pregnancy occurs during treatment, withdraw from the trial;
- Unauthorized use of drugs prohibited by this research (see "5.3 Concomitant medication");

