3.3.2 Determination of the number of cases

It is estimated that 1-year relapse-free survival is 0.56 in MMF Group, and 0.70 in FK506 Group. The enrollment time of this research is expected to be 2 years, and the total time of this research is 3 years, with a test level $\alpha = 0.05$, and a power of test $1 - \beta = 80\%$. It is estimated to have 114 patients in MMF group and 115 patients in FK506 group, with a total of 229 patients (see Appendix 4 for details). With the consideration of 15% loss of follow-up, a total of 270 patients are needed, including 135 patients in each group.

4. Selection of cases

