4.5 Drop-out and treatment

4.5.1 Definition of drop-out: All patients who have completed the Informed Consent Form and screened to be enrolled in the trial have the right to withdraw at any time. Whenever and for whatever reason, subjects who fail to complete the observation period specified in the Protocol are considered as drop-out cases, including the following situations:

- The subject has serious adverse events and the clinician believes that he/she should withdraw from the clinical trial;
- The subject shows aggravated condition or has other symptoms affecting the trial observation during the trial, and the clinician believes that he/she should withdraw from the clinical trial;
- Important deviations occur in the implementation of clinical trial protocol, such as poor compliance, which would cause difficulty in evaluating the drug effect;
- The subject is unwilling to continue the clinical trial and asks to withdraw from the clinical trial, or loss of follow-up has occurred although no request to withdraw from the trial is proposed.

4.5.2 Treatment of drop-off cases: The investigators shall contact the drop-off subjects by means of visiting, making an appointment for follow-up, calling, letter and so on, to ask the reasons, record the last medication time and complete the evaluation items that can be completed. For the cases withdrawing from the trial due to allergy or other adverse reactions and ineffective treatment, the investigators shall take corresponding treatment measures according to the actual situation of the subjects. The investigators shall properly keep the relevant test data of the drop-off cases, not only for filing, but also for full analysis and statistics.

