11.2 Statistical method

11.2.1 General statistical methods

Two-sided test is adopted for all statistical tests. If the P value is less than 0.05, the tested difference will be considered “statistically significant” (unless otherwise specified).

Descriptive analysis: Sort out and summarize a large number of data obtained from the survey to find out the internal law of these data - centralized trend and decentralized trend. Single factor analysis is mainly carried out with the help of statistics represented by various data, such as mean and percentage.

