11.3.2 Effectiveness analysis

All effectiveness analysis/global indicators will be based on ITT principles, and FAS is adopted, for only the adjudicated endpoint events. The investigators are required to report all the potential endpoint events in eCRF.

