8.1.3. Primary efficacy analysis

Logrank test is used for the analysis of relapse-free survival rate which is then used as a covariate for stratification by Sites. HR and its 95% confidence interval (CI) are calculated with Cox proportional hazard model to estimate the efficacy, the confidence interval is applied to verify the superiority of the experimental group and the control group, with a cut-off value of 1 (risk ratio). The model incorporates the same covariate as the Logrank test for fitting, and the definition method of covariates is also the same as that in the Logrank test. The Kaplan-Meier curve of relapse-free survival is drawn by treatment groups. The 1-year relapse-free survival rate and its confidence interval are then calculated.

Calculation rules for the main efficacy indicators:

- If relapse occurred within 9 visits (within 364 ± 7 days) or unscheduled visits within 365 days of randomization, defined as the occurrence of endpoint events. Time of relapse = date of relapse - Random date + 1, calculated by days.
- If the visit stipulated in the protocol was not completed within 9 visits (within 364 ± 7 days) due to loss of follow-up midway or withdrawal or other reasons, it is defined as censoring. Time of

censoring = date of withdrawal - random date + 1, calculated by days.

- If the visit stipulated in the protocol was not completed within 9 visits (within 364 ± 7 days) due to death in the trial, it is defined as censoring. Time of censoring = Death date - random date + 1, calculated by days.
- If the visit stipulated in the protocol was completed and there is no relapse within 9 visits (within 364 ± 7 days), it is defined as censoring. Time of censoring = date of visit 9 (within 364 ± 7 days) - random date + 1, calculated by days.

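### The stated ITT analysis is not supported: Protocol 4.4 ends research participation after 14 days off drug, no later relapse follow-up is scheduled, and the SAP censors at withdrawal.

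*Protocol*

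**What the plan says.** Protocol 4.4 (SAP 4.5.4) introduces ten conditions with "Patients must withdraw from this research in the following conditions". The object is the research, not the drug. One condition is "No administration of the test drug according to the Protocol for 14 consecutive days due to various reasons". Others are a target concentration still missed after a month of dose adjustment, creatinine and liver values, unacceptable adverse events, prohibited drugs, and eligibility violations. The concentration condition can apply to a child who is still taking the drug. The liver condition treats stopping the drug and leaving the trial as two separate steps.

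For children who leave, Protocol 4.5.2 asks investigators to make contact, ask the reason, "record the last medication time and complete the evaluation items that can be completed", and keep the data for analysis. It sets no schedule and no end date, and the flow chart has no visit after withdrawal.

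SAP 8.1.3 gives two rules that matter here. The first counts a relapse at a visit up to Visit 9, or at an unscheduled visit within 365 days of randomisation, as an event. The second censors a child who withdraws or is lost, with time equal to "date of withdrawal - random date + 1, calculated by days".

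Protocol 11.1 and SAP 7.1 define the FAS without eliminated cases. Protocol 4.3 includes among these children with compliance below 80% or above 120% and children who do not complete follow-up as planned. Protocol 11.3.2 (SAP 8.1.2) states: "All effectiveness analysis/global indicators will be based on ITT principles", using the FAS.

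**The concern.** An ITT comparison asks what happens to all children assigned to tacrolimus or to MMF, whether or not they stay on the drug. That needs relapse status to the end of the year for children who stop. Here a lasting stop ends participation, relapse afterwards is not systematically collected, and the SAP's second rule would discard it even if it were recorded.

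The primary result is then relapse while still in the study. It can be read as relapse under assignment only if the children who leave would have relapsed at the same rate as those who stay. The exit triggers are toxicity, exposure and adherence, so this cannot be presumed. The triggers may also fall unevenly. The Protocol flow chart schedules tacrolimus levels at seven visits and mycophenolic acid levels at two. Section 8.1.1 lists kidney injury as very common with tacrolimus, whereas the Background describes MMF as free of nephrotoxicity. At stake is whether the trial answers the question of which drug to start.

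**Working it through.** **Plan's own figures.** Inputs: "1-year relapse-free survival is 0.56 in MMF Group, and 0.70 in FK506 Group" (Protocol 3.3.2), 2 years of accrual in 3 years total, and 114 + 115 children. With constant hazards:

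- hM = −ln 0.56 = 0.5798 and hF = −ln 0.70 = 0.3567, so HR = 0.3567/0.5798 = 0.6151, as in Appendix 4.
- Event probability = 1 − [exp(−h·1) − exp(−h·3)]/(2h). Expected events are 76.2 + 57.4 = 133.7 after rounding (stated 133.8), with power 0.80 (stated 0.8009).
- 229/0.85 = 269.4, hence 270, or 135 per arm.

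The 15% is an allowance for loss to follow-up. It is not a rate of exits under 4.4.

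**Assumptions not in the documents.** A fraction f would exit over one year, at constant hazard e = −ln(1 − f). After exit, children in both arms relapse at a common hazard u of 1 to 2 per year, which is a 1-year risk of 63% to 86%. Exits are independent of a child's own relapse risk. Under these assumptions the censored curve still shows 0.70 − 0.56 = 14 points.

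**Formula.** Relapse-free at 1 year with everyone followed:

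S = exp(−(h+e)) + [e/(h+e−u)]·[exp(−u) − exp(−(h+e))]

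**Worked case, f = 15% in both arms, u = 1.** e = 0.1625.

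- MMF: h+e = 0.7423. S = 0.4760 + (0.1625/−0.2577)(0.3679 − 0.4760) = 0.4760 + 0.0682 = 0.544.
- Tacrolimus: h+e = 0.5192. S = 0.5950 + (0.1625/−0.4808)(0.3679 − 0.5950) = 0.5950 + 0.0768 = 0.672.
- Difference: 12.8 points.

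**All cases (u = 1 to u = 2).**

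| Exits MMF / tacrolimus | MMF S | Tacrolimus S | Difference, points |
|---|---|---|---|
| 5% / 5% | 0.555–0.547 | 0.691–0.682 | 13.6–13.5 |
| 15% / 15% | 0.544–0.520 | 0.672–0.645 | 12.8–12.5 |
| 10% / 20% | 0.550–0.534 | 0.662–0.627 | 11.2–9.3 |
| 20% / 10% | 0.539–0.506 | 0.681–0.664 | 14.3–15.8 |

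Differences are taken before rounding.

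**Children affected at 15% per arm.** The probability of leaving relapse-free is [e/(h+e)]·[1 − exp(−(h+e))]: 0.1147 for MMF and 0.1268 for tacrolimus. Times 135, that is 15.5 + 17.1, about 33 children.

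**Rules side by side.** Suppose a child withdraws and a relapse is later found at an unscheduled contact within 365 days. Rule 1 of SAP 8.1.3 makes this an event, because it does not require the child to be on drug. Rule 2 censors the same child at withdrawal. The SAP does not say which rule prevails.

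**The case against.** Four stronger readings are tempting, and the documents do not support them.

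- **Every child who stops the drug must leave.** The trigger is 14 consecutive days, so shorter interruptions stay in. The liver condition stops the drug first and requires withdrawal only if there is no recovery after two weeks.
- **Relapse after stopping is never observed.** Section 4.5.2 asks for contact, whatever evaluations are possible, and use of the data. Protocol 11.3.5 mentions efficacy in long-term follow-up after the trial. Collection is unscheduled and incomplete, but not absent.
- **The fault lies only in data collection, so no ITT analysis could ever be made.** Rule 1 would count a recorded relapse. Part of the fault is the conflict with Rule 2, and part is the FAS definition.
- **A large bias in a known direction has been shown.** At 15% exits in both arms the shift is 1.2 to 1.5 points, and at 5% about half a point. The larger shifts need a 20%/10% split that no section supports, and their direction depends on which arm loses more. Children who are lost or withdraw consent would be missing under any plan, so only part of the 15% is recoverable.

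The model also makes exits independent of a child's own relapse risk. It therefore measures the gap between two target quantities, not the effect of selective exit. It is also fair to say that relapse while on study is a legitimate quantity to estimate. These limits stand. None of them makes the planned analysis ITT, which is what both documents say it is.

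**Conclusion.** The point holds. Protocol 4.4 and SAP 4.5.4 require leaving the research after 14 days off drug and for other drug-related reasons. Relapse follow-up to Day 364 is not scheduled after that, SAP 8.1.3 censors at withdrawal, and the FAS removes eliminated children. The ITT statement is therefore not supported. The primary result is relapse while still in the study, and it relies on non-informative censoring.

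The size is unknown. Under the assumptions above, the all-randomised difference ranges from 9.3 to 15.8 points against 14 on the censored curve. With 15% exits per arm, which is the plan's loss allowance taken as an upper proxy, it is 12.5 to 12.8. The change should be made because the label and the data disagree and the remedy is cheap, not because a large bias has been demonstrated.

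**What to change.** 1. **Protocol 4.4, 4.5.2 and SAP 4.5.4:** separate end of study drug from end of observation, leaving every clinical stopping condition unchanged. Unless consent to follow-up is withdrawn, keep the child on the flow-chart visits to Visit 9 for relapse, steroid dose, renal function and adverse events. Section 4.4 lists conditions for leaving the research, so the sponsor should state for each one whether it also ends the drug.
2. **SAP 8.1.3:** resolve the conflict between the first two rules so that relapses within the year after drug stop count in the primary analysis. Keep censoring at drug stop or withdrawal as a supportive analysis.
3. **Protocol 11.1 and SAP 7.1:** stop excluding randomised children from the FAS for non-compliance or incomplete follow-up, and exclude them from the PPS only. Without this step, a child followed to Visit 9 off drug could still be dropped from the primary set.
4. **If follow-up can no longer be collected:** drop the ITT label and describe the estimate as relapse while on study.

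The cost is wording in these sections and the use of visits already planned for each child. The downside is small: sites must keep contact with children off drug, and relapses under later non-trial treatment enter the result.
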